7.2.2.5. CKD Stage

CKD stage will be summarized over time by presenting the number and proportion of patients that improved (excluding those with Stage 1 at baseline as they cannot improve), worsened (excluding those with Stage 5 at baseline as they cannot worsen), and stayed the same compared to CKD stage at baseline. Stage 5 will be considered the worst category, while stage 1 will be considered the best category (see [Section 9.4.11](#) for details). A 2-sided 95% CI for each proportion will be provided. The CIs will be based on exact confidence limits using the Clopper-Pearson method. This summary will be repeated by the kidney transplant status at enrollment.

7.2.2.6. Hematologic Parameters

Hematologic parameters (platelets, LDH, hemoglobin) will be summarized at baseline and each postbaseline time point using descriptive statistics for continuous variables for the observed value as well as the change from baseline. This summary will be repeated on the PPS. As suggested in [Section 7.2.2.4](#), a mixed model for repeated measures (MMRM) will be used to improve the precision of estimation of changes over time.

Figures presenting the observed values and the model based values over time for these hematologic parameters will be provided.

7.2.2.7. Hemoglobin Response

The number and proportion of patients with an increase from baseline in hemoglobin $\geq 20\text{g/L}$, observed at 2 separate assessments obtained at least 4 weeks (28 days) apart, and any measurement in between will be summarized over time by presenting the number and proportion of responders along with a 2-sided 95% CI for each postbaseline time point.

A patient will be included in the analysis for a specific postbaseline time point if it was possible for the result at that time point to be confirmed (ie, the patient has to be in the study for a subsequent confirmatory assessment at least 28 days later). For example, a patient on-study at the Day 71 assessment and at the Day 99 assessment would be included in the Day 71 summary. However, a patient on-study at the Day 71 assessment that did not remain on-study until the Day 99 assessment or later would not be included in the Day 71 summary.

A set of summaries similar to the ones described above will be created without any requirement for a confirmatory result. This summary will be strictly based on a patient meeting the criterion at a specific time point.

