- Patients who satisfy Exclusion Criterion number 2

The FAS will be determined prior to database lock and prior to the database snapshot for the analysis performed at the end of the 26-week Initial Evaluation Period.

Primary efficacy:

The primary efficacy endpoint is Complete TMA Response during the 26-week Initial Evaluation Period. The primary analysis will consist in estimating the proportion of complete TMA responders among ALXN1210 treated patients. This will be performed by calculating the point estimate and a 95% CI for the proportion of complete TMA responders in ALXN1210 treated patients. The CI will be based on the asymptotic Gaussian approximation method with a continuity correction.

Secondary efficacy:

For the secondary efficacy endpoint of time to Complete TMA Response, a Kaplan-Meier cumulative distribution curve will be generated along with a 2-sided 95% CI. The corresponding summary table will present the cumulative distribution function (CDF) estimate, the number of patients at risk, the number of patients responding, and the number of patients censored at each postbaseline time point. The table will also present first quartile,

median, and third quartile, along with corresponding 2-sided 95% CI, of time to complete response.

Complete TMA response will also be summarized over time by presenting the number and proportion of responders along with a 2-sided 95% CI for each postbaseline time point. A similar approach will be used to summarize the number and proportion of patients with an increase from baseline in hemoglobin ≥ 20 g/L, observed at 2 separate assessments obtained at least 4 weeks (28 days) apart, and any measurement in between.

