9.7. Prohibited Medications and Procedures

Patients are prohibited from receiving any of the following medications and procedures at any time after the first dose of study drug for all patients in the study (even those who discontinue ALXN1210 treatment but remain in study) until completion of the study or early termination of the patient from the study:

- Eculizumab or other complement inhibitors
- Use of any other investigational drug or device as part of a clinical trial.
- IVIg (unless for an unrelated medical need e.g. hypogammaglobinemia)
- Rituximab
- PE/PI
- New dialysis within the first 48-hour period following the first dose of ALXN1210 unless there is a compelling medical need as assessed by (1) hypervolemia unresponsive to diuretics, (2) refractory electrolyte imbalance, or (3) new-onset uremic encephalopathy. Exceptions must be approved prior to administration of dialysis on a case-by-case basis by the Sponsor.

The following concomitant medications and procedures are allowed under certain circumstances and with the following restrictions:

- Use of other immunosuppressive therapies (such as steroids, mTORi [eg, sirolimus, everolimus], CNI [eg, cyclosporine or tacrolimus]) during the study are not allowed unless: a) part of an established post-transplant antirejection regime, or b) patient has

confirmed anti-complement factor antibodies requiring immunosuppressive therapy, or c) steroids are being used for a condition other than aHUS (eg, asthma), or d) steroids initiated empirically prior to enrollment and are being tapered as standard of care.

Any patients receiving other complement inhibitors (including eculizumab) or undergoing PE/PI after the first dose of study drug will be withdrawn from the study.

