15.8.2.7. Hemoglobin Response

The number and proportion of patients with an increase from baseline in hemoglobin ≥ 20 g/L, observed at 2 separate assessments obtained at least 4 weeks (28 days) apart, and any measurement in between, will be summarized over time by presenting the number and proportion of responders along with a 2-sided 95% CI for each postbaseline time point.

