7.2.1. Primary Analysis

The primary efficacy endpoint is Complete TMA Response during the 26-week Initial Evaluation Period. The primary analysis will consist in estimating the proportion of complete TMA responders among ALXN1210 treated patients. This will be performed by calculating the point estimate and a 2-sided 95% confidence interval (CI) for the proportion of complete TMA responders in ALXN1210 treated patients, where the numerator will be the number of patients achieving complete TMA response during the 26-week Initial Evaluation Period and the denominator will be the number of patients in the FAS. The CI will be based on the asymptotic Gaussian approximation method with a continuity correction.

The criteria for Complete TMA response are presented in [Section 5.1.1](#). Patients must meet all Complete TMA Response criteria at 2 separate assessments obtained at least 4 weeks (28 days) apart, and any measurement in between. To be considered a responder during the 26-week Initial Evaluation Period, the latest time point a patient can first meet the response criteria is 28 days before the Day 183 assessment.

Formal statistical comparison analyses are not planned for this estimation study. Results from ALXN1210 treated patients will be evaluated in the context of results observed in patients treated with eculizumab in prospective eculizumab studies.

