7.2.1.1. Handling of Dropouts or Missing Data

For evaluation of Complete TMA Response during the 26-week Initial Evaluation Period (primary endpoint), patients missing an efficacy assessment that is part of the definition of Complete TMA Response while still on-study, will have their last observation carried forward (LOCF). For patients who will have discontinued from the study prior to Week 26, their data up to the time of discontinuation will be used to assess Complete TMA Response. A confirmatory result cannot be from an assessment that was carried forward from the initial assessment when all Complete TMA Response criteria were met.

For laboratory data, in the event of duplicate samples from local and central laboratories (for any time point), central laboratory results will be used for analysis.

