7.2.2.2. Time to Complete TMA Response

For the secondary efficacy endpoint of time to Complete TMA Response, Kaplan Meier cumulative distribution curves will be generated along with 2-sided 95% CIs. The corresponding summary table will present the cumulative distribution function (CDF) estimate, the number of patients at risk, the number of patients responding, and the number of patients censored at each postbaseline time point. The table will also present first quartile, median, and third quartile, along with corresponding 2-sided 95% CI, of time to complete response.

Complete TMA response is defined in [Section 5.1.1](#). Patients must meet all Complete TMA Response criteria at two separate assessments obtained at least 4 weeks (28 days) apart, and any measurement in between. The time of the event of a confirmed complete TMA response will be considered as the first time point at which all the criteria for complete TMA response were met.

Patients that did not have a response will be censored at the date of last visit or study discontinuation at the time when the analysis is performed.

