7.2.2.3. Complete TMA Response Status Over Time and Alternative Definitions

Complete TMA Response will also be summarized over time by presenting the number and proportion of responders along with a 2-sided 95% CI for each postbaseline time point. This summary will be accompanied by a similar presentation for the components of complete TMA response: proportion of patients with platelet count normalization, proportion of patients with LDH normalization, proportion of patients with hematologic normalization (platelet count and LDH), proportion of patients with $\geq 25\%$ improvement in serum creatinine from baseline. The CIs will be based on the asymptotic Gaussian approximation method with a continuity correction. These tabular summaries will be accompanied by a bar chart graphical figure displaying for each time point a bar for Complete TMA Response and each component in its definition, where the bar will represent the proportion of patients meeting that specific criterion.

A patient will be included in the analysis for a specific postbaseline time point if it was possible for the result at that time point to be confirmed or to serve as a confirmatory result.

A set of summaries similar to the ones described above will be produced without any requirement for a confirmatory result. This summary will be strictly based on a patient meeting the criterion at a specific time point.

A slightly modified version of complete TMA response will also be evaluated. The modification will only affect patients considered to be on dialysis at baseline (ie. patients requiring dialysis within 5 days prior to ALXN1210 treatment initiation). For these patients, the criterion requiring

an improvement from baseline of 25% or more in serum creatinine, will be replaced by a postbaseline change in dialysis status (from requiring dialysis at baseline to no longer requiring dialysis) that is maintained for at least 4 weeks. A set of summaries similar to the ones described above will be produced based on this alternative definition.

The tabular summary of complete TMA response over time will also be performed on the PPS.

7.2.2.4. eGFR Value and Change from Baseline

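### By-visit confirmed hemoglobin response and time to Complete TMA Response both depend on who stays in the study; the primary analysis is largely protected

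*SAP*

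**What the plan says.** - **Hemoglobin (SAP 7.2.2.7).** A patient enters a visit's confirmed summary only if in the study for an assessment at least 28 days later. In the worked example, "a patient on-study at the Day 71 assessment that did not remain on-study until the Day 99 assessment or later would not be included" at Day 71. A parallel summary without confirmation is also planned.
- **Complete TMA Response over time (SAP 7.2.2.3).** The inclusion rule is wider. A patient is counted at a visit "if it was possible for the result at that time point to be confirmed or to serve as a confirmatory result".
- **Time to Complete TMA Response (SAP 7.2.2.2).** "Patients that did not have a response will be censored at the date of last visit or study discontinuation". No exception is made by reason for leaving.
- **Primary (SAP 7.2.1 and 7.2.1.1).** The denominator is the whole FAS. For early leavers, "their data up to the time of discontinuation will be used to assess Complete TMA Response". There is also a cut-off: "the latest time point a patient can first meet the response criteria is 28 days before the Day 183 assessment". SAP 7.2.2.2 has no such cut-off.
- **Withdrawals (Protocol 9.7 and 8.3.1).** Patients given another complement inhibitor or "undergoing PE/PI after the first dose of study drug will be withdrawn from the study". Transplant patients with antibody-mediated rejection for whom rituximab is judged appropriate also leave the study.

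**The concern.** Under 7.2.2.7, whether a patient is in the denominator at a visit depends on what happens afterwards. Leaving is partly tied to outcome, because the protocol removes patients for rescue-type therapy. The by-visit rate is then a rate among those who remained, not among the treated FAS.

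The Kaplan-Meier analysis has a related problem. A censored patient is credited with the same later chance of response as a patient still followed. For someone who died that chance is zero, and for someone withdrawn for rescue no response on study drug can be observed.

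The study estimates and does not test (SAP 7.2.1.4), and its results are to be read alongside eculizumab studies (SAP 7.2.1). The descriptive figures are therefore its product. The report could show a Kaplan-Meier percentage at Day 183 above the primary proportion for the same responders.

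**Working it through.** The plan gives no figure for either analysis, no hemoglobin response rate and no breakdown of reasons for leaving. Its only relevant figures are in SAP 9.3: 65% response, 50 evaluable patients, 10% drop-out and 55 enrolled. They reproduce acceptably. The half-width is 1.96 × √(0.65 × 0.35/50) = 13.2%, or 14.2% with the continuity correction (+1/100), against a stated figure of about 15%. Also 50 × 1.10 = 55. Everything below is illustration.

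**1. Which visits count.** The visits in Protocol Table 1 are Days 8, 15, 22, 29, 43, 57, 71, 85, 99, 113, 127, 141, 155, 169 and 183. Visit v counts only if an assessment exists at v + 28 or later. The Early Termination visit is taken as an assessment, which the SAP does not state.

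| Last assessment | Visits attended | Visits counted |
|---|---|---|
| Day 29 | 4 | 0 |
| Day 43 | 5 | 2 |
| Day 57 | 6 | 4 |
| Day 99 | 9 | 7 |
| Day 155 | 13 | 11 |

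A patient last assessed at Day 29 is in no denominator. Within the Initial Evaluation Period, one last assessed at Day 57 or later loses the last two visits.

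**2. The 28-day rule alone.** Assume 22 to 39 of 55 respond at a visit and everyone is still present at it.
- One non-responder leaves in the next 28 days: 22/54 = 40.7% v 22/55 = 40.0% (+0.7); 39/54 = 72.2% v 39/55 = 70.9% (+1.3).
- Two leave: 22/53 = 41.5% (+1.5); 39/53 = 73.6% (+2.7).
- If one leaver is instead a responder whom that visit had just confirmed: 21/54 = 38.9% (−1.1); 38/54 = 70.4% (−0.5).

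**3. Full FAS comparison.** Planned drop-out is 10% of 55 = 5.5.
- Six cumulative non-responding leavers: 22/49 = 44.9% (+4.9); 39/49 = 79.6% (+8.7).
- Five: 22/50 = 44.0% (+4.0); 39/50 = 78.0% (+7.1).
- All six leavers confirmed responders, compared with a line that keeps their status: 16/49 = 32.7% v 40.0% (−7.3); 33/49 = 67.3% v 70.9% (−3.6).

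**4. Time to response.** Assume 36 of 55 respond (65.5%, the nearest count to 65%) and 5 non-responders leave.
- All leave after the last response: Kaplan-Meier 36/55 = 65.5%.
- All leave after 18 responses: 1 − (37/55)(14/32) = 70.6%.
- All leave before the first response: 36/50 = 72.0% (with six leavers, 36/49 = 73.5%).
- Cumulative incidence with all 5 as competing events: 36/55 = 65.5%, whatever the timing.
- Cumulative incidence with 2 competing and 3 censored: 65.5% up to (53/55)(36/50) = 69.4%.

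**5. Cut-off.** The nominal limit is 183 − 28 = Day 155. A patient first meeting the criteria at Day 169 needs confirmation at Day 197 or later, so at the Day 239 visit in the Extension Period. That patient is an event before Day 183 on the curve but a primary non-responder. Each such patient adds 1/55 = 1.8 points when nobody has left (37/55 = 67.3%).

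**The case against.** A reader might infer that the 28-day rule by itself inflates hemoglobin response by 5 to 9 points. It does not. Most of the step 3 gap comes from patients already gone, whom any observed-data table would also lack. If six leave evenly over 183 days, the rule removes about 6 × 28/183 = 0.9 further patients at a visit. Six leavers would also leave 49, below the planned 50 evaluable. The direction is not fixed either. Comparing the planned rate with one that scores departed responders as non-responders proves nothing, since the numerator is the same and the denominator smaller.

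A reader might also infer that the SAP contradicts the protocol. The documents do not support that. The synopsis says "A similar approach will be used to summarize the number and proportion of patients with an increase from baseline in hemoglobin", and Protocol 15.8.2.7 says the result "will be summarized over time by presenting the number and proportion of responders along with a 2-sided 95% CI for each postbaseline time point". Both concern presentation. Neither sets a denominator, and Protocol 15.1 leaves details to the SAP.

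Nor is the curve wrong for lacking the primary's cut-off, because Protocol 6.2.2 has secondary endpoints measured through 26 weeks and over the whole study. Its table will show numbers at risk and censored. SAP 7.2.2.2 does not name death or rescue; their censoring is inferred from a general rule.

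Other protections are real. Stopping drug is not leaving the study (Protocol 8.3.2), and unconfirmed hemoglobin response, repeated-measures models and listings are planned. All of this stands and limits the importance. What remains is that none of those outputs gives confirmed hemoglobin response in the full FAS, and none separates death or rescue from ordinary censoring.

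**Conclusion.** The point holds in a limited form. SAP 7.2.2.7 makes each visit's denominator depend on later retention and is narrower than SAP 7.2.2.3. SAP 7.2.2.2 treats all departures without response as ordinary censoring. Both affect description only.

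Under the assumed counts, the hemoglobin rule alone moves a visit's rate by roughly 1 to 3 points for one or two non-responding leavers. The larger gap against the FAS requires six who never responded. The Kaplan-Meier excess over the primary runs from 0 to 6.5 points (72.0 − 65.5) with five non-responding leavers, depending on timing, before any late responses confirmed in the Extension Period.

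It would be wrong to read this as a fault in the primary. A leaver without confirmed response stays in its denominator as a non-responder. The one gap is a treated patient lost before any postbaseline efficacy assessment, who is outside the FAS (SAP 6.1).

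**What to change.** **Hemoglobin (SAP 7.2.2.7)**
- Use the full FAS as denominator at each visit through Day 155. Let a visit count if it is confirmed or serves as the confirming result, as in 7.2.2.3.
- Count patients who have died or left the study as non-responders at visits after departure, and a last result that cannot be confirmed as non-response.
- Add a sensitivity line in which already confirmed responders who leave keep that status. This is not the main line, because patients who stay can lose response at a later visit.
- For patients still on study, show values that are missing or excluded after transfusion (SAP 9.4.10) as a separate count, and apply one pre-stated rule to them. Say also where patients belong whose off-drug data Protocol 15.1 moves to listings.
- State whether an Early Termination sample can confirm, and whether the 28 days run on actual dates. Day 155 is only the nominal limit, given the visit windows.
- Keep the planned table as supplementary.

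**Time to response (SAP 7.2.2.2)**
- Keep the Kaplan-Meier curve. Add a supplementary Aalen-Johansen cumulative incidence curve with death and withdrawal for prohibited or rescue therapy as competing events.
- Add a sensitivity version with all study withdrawals as competing, because withdrawal of consent may also reflect failure.
- Footnote that the Day 183 value can differ from the primary through censoring and through responses first met after the primary's cut-off.

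Fix the classification of withdrawals before the database snapshot.

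**Cost.** No new data are needed, since the reason for early termination is already on the eCRF (Protocol 8.3.1). No objective or study conduct changes, so under Protocol 15.1 no amendment is needed and the change is described in the CSR. The price is a few table lines, one extra curve with its sensitivity version, and possibly slightly less favourable secondary figures.

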7.2.2.8. Quality of Life

Quality of life will be evaluated using EQ-5D-3L (all patients), FACIT Fatigue version 4 Questionnaire (patients ≥ 18 years of age), Pediatric FACIT Fatigue Questionnaire (patients < 18 years of age). These measures will be summarized at baseline and each postbaseline time point using descriptive statistics for continuous variables for the observed value as well as the change from baseline. The FACIT Fatigue results will be presented separately and combined for adults and pediatric patients. As suggested in [Section 7.2.2.4](#), a mixed model for repeated measures (MMRM) will be used to improve the precision of estimation of changes over time.

The number and proportion of patients with a 3 point improvement from baseline in the FACIT Fatigue score will be summarized over time by presenting the number and proportion of patients along with a 2-sided 95% CI for each postbaseline time point.

Figures presenting the observed values and the model based values over time for these quality of life assessments will be provided.

7.2.3. Exploratory Analyses

Resource Utilization Questionnaire (all patients) data will be summarized at each postbaseline assessment using discrete data summary statistics.

Patient-reported aHUS Symptoms Questionnaire (all patients) data will be summarized at each postbaseline assessment by presenting the number and proportion of patients with a specific symptom present. Extra-Renal Signs and Symptoms of aHUS data will be presented similarly.

These data will also be presented in detailed by-patient listings.

7.2.4. Other Efficacy Analyses

Not applicable.

7.2.5. Pharmacokinetic and Pharmacodynamic Analyses

All Pharmacokinetic and Pharmacodynamic analyses will be summarized prospectively in a separate analysis plan.

7.3. Safety Analyses

All safety analyses will be conducted on the Safety Set. All safety data will be provided in patient listings. AEs will be coded in MedDRA version 18 or higher and presented by MedDRA system organ class (SOC) and preferred term. All safety analyses will be presented by age category (12-17, 18 years of age and up) except for immunogenicity and physical examination summaries. No formal hypothesis testing is planned.

